## 5. STATISTICAL METHODOLOGY

### 5.1. GENERAL METHODOLOGY

Demographics and work-related variables will be reported with means and standard deviations for continuous variables (e.g., age) and as frequencies for categorical variables (e.g., gender). Items of questionnaires (e.g., Sense of Coherence Scale) will be recoded (where applicable) and a scale mean or sum score will be calculated in data processing. Means/sum scores and standard deviations will be reported separately by treatment group.

If applicable, means and standard deviations of user statistics will be calculated and reported (e.g., means among the subgroup of users who completed a specific module).

For continuous outcomes, we will use  $t$ -tests for independent samples and for categorical outcome we will employ  $\chi^2$ -tests to examine baseline differences between training and control group in demographic data or measured variables.

#### HANDLING OF MISSING DATA

- On the one hand, the data will be analysed according to the "intention-to-treat" principle, with missing values being replaced using appropriate imputation methods.
- On the other hand, the results will be reported as "per-protocol" analysis, in which only those cases are considered that have gone through the study procedure as defined by protocol. We consider the intervention to be completed for participants who, in addition to the theory modules, completed at least 50% of the weekly interventions and the daily training interventions. To note, a maximum of 4 weekly interventions with 6 daily interventions can be reached. In the per-protocol analysis, only these participants will be included. To control for influences of compliance, usage of intervention will be examined as covariate in an exploratory analysis.

#### CLASSIFICATION OF PROTOCOL VIOLATION

Exclusion of participants due to protocol violations will be reported in the methods / results section. To examine outliers in the questionnaire data, boxplots will be created.

### 5.2. PRIMARY AND SECONDARY DATA ANALYSES

In primary and secondary data analyses, all stated hypotheses will be tested. In all analyses an error probability of  $\alpha = .05$  will be set a priori for interference statistics calculations. In cases of multiple testing,  $\alpha$  will be adjusted accordingly. In addition to statistical significance, descriptive statistics and effect sizes (e.g., Cohen's  $d$ ) will be reported. Publication of results will follow CONSORT guidelines for transparent reporting of randomized trials.

Cronbach's  $\alpha$  and McDonald's  $\omega$  will be calculated as measure of reliability of the respective questionnaires.

Before data analysis, assumptions of statistical methods (e.g., variance of homogeneity, normal distribution) will be tested with suitable procedures (e.g., Levene-tests, Box's M, histograms, QQ-plots, and Shapiro-Wilk-Test). Zero-order correlations between study variables will be reported. Non-parametric correlation calculation will be based on results of (non-)normality, etc. Variables will be standardized where applicable.

The analysis plan for H1 to H11 is as follows:

- Differences between study groups in primary and secondary outcomes before ( $t_0$ ) and after the intervention ( $t_2$ ) and at the time of the first follow-up ( $t_3$ ) will be examined using mixed analyses of covariance (ANCOVA), with group (intervention vs. waitlist-control) as a between-subjects factor, time ( $t_0$ ,  $t_2$ ,  $t_3$ ) as a within-subjects factor and pre-measurement ( $t_0$ ) included as a covariate to increase test power. Outcomes will be the primary outcome resilience (measured with SR Score) and the secondary outcomes resilience (measured with BRS), perceived stress, self-care, self-compassion, mindfulness, mental health, depression, anxiety, burnout, and work-life-balance, respectively.
- If applicable, post-hoc  $t$ -tests will be conducted.
- Effect sizes will be calculated for the ANCOVA (i.e.,  $\text{Eta}^2$ ) as well as for between-group differences (i.e., Cohen's  $d$ ) at post-intervention assessment ( $t_2$ ) and the first follow-up assessment ( $t_3$ ). Also, the effect size of the intervention effect will be calculated (i.e., Cohen's  $d$ ).

The analysis plan for H12 is as follows: term effect over the follow-up measurements ( $t_0$  to  $t_5$ ) within the intervention group will be tested using a repeated measures ANOVA.

- If applicable, post-hoc  $t$ -tests and planned contrasts will be conducted.
- Effect sizes will be calculated.
- $\text{Eta}^2$  will be calculated as measure for effect size for the ANOVA.

The analysis plan for H13 and H14 is as follows:

- In order to test whether the changes in the state measurements (pre- to post-intervention in state self-compassion and state self-care) are significant, we will conduct within-group  $t$ -tests. We will perform separate tests for state self-compassion and state self-care, each for (1) the weekly training interventions and (2) the first practice of daily interventions, respectively.
- Cohen's  $d$  will be calculated as measure for effect size.

The analysis plan for H15 is as follows:

- Linear regressions will be conducted with the following predictor and criterion variables:
  - Predictor variables:
    - baseline-values of self-care (and, in separate models, self-compassion / resilience / burnout, respectively) at  $t_0$
    - amount of interventions completed (number of weekly training interventions and daily interventions)

- Criterion variables:
  - Post-intervention values of self-care (and, in separate models, self-compassion / resilience / burnout, respectively) at  $t_2$

If assumptions for the mentioned statistical methods are violated, appropriate non-parametric statistical methods will be chosen.

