### 2.5. SAMPLE SIZE

Previous studies from our research groups have shown a medium to large effect size for the stressor reactivity score as a primary outcome measure in online intervention studies for resilience (AG [name], unpublished). Because a large effect size was found only in a particularly stressed population, which is not expected in the sample addressed here, we assume a medium effect here (Hedges'  $g = .50$ ). Therefore, the sample size design was calculated with a medium effect size, a significance level of 0.05 and a power of 0.90 using G\*Power (Faul et al., 2007). This results in a required sample size of  $n = 74$  per group ( $N = 146$ ). As there are high dropout rates for online interventions (van Ballegooijen et al., 2014) we decided to recruit  $n = 120$  individuals per group. This number is based on an assumed dropout rate of 40%.

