**4.4. Hypotheses**

1. The intervention will significantly increase resilience, measured with the SR Score, in the intervention group (IG) compared with a waitlist control (WLC) group at  $t_2$  and  $t_3$  compared to  $t_0$ .
2. The intervention will significantly increase resilience, measured with the Brief Resilience Scale, in the intervention group (IG) compared with a waitlist control (WLC) group at  $t_2$  and  $t_3$  compared to  $t_0$ .
3. The intervention will significantly increase self-care in the intervention group (IG) compared with a waitlist control (WLC) group at  $t_2$  and  $t_3$  compared to  $t_0$ .
4. The intervention will significantly increase self-compassion in the intervention group (IG) compared with a waitlist control (WLC) group at  $t_2$  and  $t_3$  compared to  $t_0$ .
5. The intervention will significantly increase mindfulness in the intervention group (IG) compared with a waitlist control (WLC) group at  $t_2$  and  $t_3$  compared to  $t_0$ .
6. The intervention will significantly reduce perceived stress in the intervention group (IG) compared with a waitlist control (WLC) group at  $t_2$  and  $t_3$  compared to  $t_0$ .
7. The intervention will significantly increase mental health in the intervention group (IG) compared with a waitlist control (WLC) group at  $t_2$  and  $t_3$  compared to  $t_0$ .
8. The intervention will significantly reduce depressive symptoms in the intervention group (IG) compared with a waitlist control (WLC) group at  $t_2$  and  $t_3$  compared to  $t_0$ .
9. The intervention will significantly reduce anxiety symptoms in the intervention group (IG) compared with a waitlist control (WLC) group at  $t_2$  and  $t_3$  compared to  $t_0$ .
10. The intervention will significantly reduce burnout symptoms in the intervention group (IG) compared with a waitlist control (WLC) group at  $t_2$  and  $t_3$  compared to  $t_0$ .
11. The intervention will significantly increase work-life-balance in the intervention group (IG) compared with a waitlist control (WLC) group at  $t_2$  and  $t_3$  compared to  $t_0$ .
12. In the intervention group, the intervention will lead to improved resilience by the end of the intervention (at  $t_2$ ) and these improvements should be maintained at the respective follow-ups (at  $t_3$ ,  $t_4$ ,  $t_5$ ; probably to a lesser degree).
13. Self-compassion interventions (weekly intervention and daily training intervention) in the practice modules:

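### The H1 to H11 model uses t0 both as outcome level and as covariate, with no t0-by-time term stated, and the contrast that decides H1 is not named

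*SAP*

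**What the plan says.** SAP section 5.2 gives one model for H1 to H11: a mixed ANCOVA with "group (intervention vs. waitlist-control) as a between-subjects factor", and with "time ( $t_0$ , $t_2$ , $t_3$ ) as a within-subjects factor and pre-measurement ( $t_0$ ) included as a covariate". The reason given for the covariate is power: "included as a covariate to increase test power". No interaction is written down, neither group-by-time nor t0-by-time.

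Section 4.4 words H1, and likewise H2 to H11, as a benefit in the intervention group "compared with a waitlist control (WLC) group at $t_2$ and $t_3$ compared to $t_0". It attaches no model term or contrast to that statement.

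Section 5.2 then adds "If applicable, post-hoc $t$ -tests will be conducted", between-group Cohen's d at t2 and at t3, and "Also, the effect size of the intervention effect will be calculated" without saying which effect is meant. It says that alpha will be adjusted where there is multiple testing, but names neither a method nor a family of tests.

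**The concern.** There are two linked problems.

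**The covariate may do nothing for the test that matters.** A benefit over waitlist at later times relative to t0 is a group-by-time statement. A person's t0 value is the same at every time point. Entered as a main effect only, it shifts all of that person's scores equally and cancels from every within-person comparison. The aim of raising power is met for this test only if t0 is crossed with time. Because the SAP does not state that term, the primary result can depend on a software setting.

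**No rule says what counts as support for H1.** The deciding result could be the group main effect, the three-level interaction, t2 against t0, t3 against t0, or both. These answer different questions and can disagree in the same data. A significant three-level interaction does not show an effect at both t2 and t3, since it also rejects when the effect is at t2 alone.

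At stake are precision that the same data would give at no cost, and a primary conclusion that could be chosen after the results are seen.

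**Working it through.** **Inputs from the SAP.** Section 2.5: g = 0.50, alpha 0.05, power 0.90, 120 per group, 40% dropout, so 120 × (1 − 0.40) = 72 completers per group. Section 5.1: missing values are imputed in the intention-to-treat analysis, so those data are complete over time.

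**The SAP's own sample size.** Section 2.5 states 74 per group (N = 146) without naming the test. A one-sided Mann-Whitney test (efficiency 3/π) gives 73 per group, N = 146. A one-sided t-test gives 70 per group and a two-sided t-test 86. The point below does not depend on which was used.

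**Assumptions not in the SAP.** Unit-variance normal scores, two-sided tests, and correlations (t0 with each follow-up / t2 with t3) of 0.3/0.5, 0.5/0.6 and 0.6/0.8.

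**Step 1, cancellation.** Write the score of person i at time t as m(t) + c(t)·G + b·B + person effect + error, where G is group and B is the t0 value. In any difference between two times, b·B disappears, so the estimate and standard error of group-by-time do not change. With a slope b(t) that varies over time, (b(t) − b(t0))·B remains and removes variance.

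One simulated data set confirms this:
- no covariate: group-by-time F(2, 284) = 1.7174
- t0 as main effect: F(2, 284) = 1.7174
- t0 crossed with time: F(2, 282) = 5.227

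**Step 2, the group main effect.** At t0 the adjusted group difference is zero, because t0 is adjusted for itself. The three-level average is therefore (0 + d2 + d3)/3, which is two thirds of (d2 + d3)/2. In the same data set this gives 0.262 against 0.393, and 0.393 × 2/3 = 0.262. The test is unaffected (t = 3.365 in both), as is d on the residual SD (0.567 in both). Only the raw estimate is diluted.

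**Step 3, power** (20,000 simulated trials per setting, 72 per group, d = 0.5 at t2 and t3):

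| Test | 0.3/0.5 | 0.5/0.6 | 0.6/0.8 |
|---|---|---|---|
| Group-by-time, t0 main effect only, univariate | 0.760 | 0.884 | 0.943 |
| Same, multivariate | 0.700 | 0.856 | 0.895 |
| Group-by-time, t0 crossed with time, univariate | 0.903 | 0.955 | 0.977 |
| Same, multivariate | 0.911 | 0.958 | 0.957 |
| t2 and t3 both at 0.05, t0-adjusted | 0.789 | 0.880 | 0.933 |
| Holm over t2 and t3, at least one | 0.921 | 0.963 | 0.970 |
| Holm over t2 and t3, both | 0.782 | 0.876 | 0.929 |
| Average of t2 and t3, t0-adjusted | 0.954 | 0.980 | 0.981 |

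A separate simulation (4,000 trials per setting) with one common correlation of 0.3, 0.5 or 0.7 gives univariate group-by-time power of 0.74, 0.88 and 0.98 without the t0-by-time term, and 0.90, 0.96 and 0.995 with it.

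**Step 4, precision at a single follow-up.** With equal variances, the variance of the unadjusted change is proportional to 2(1 − r) and that of the t0-adjusted difference to 1 − r². The ratio is 2/(1 + r): 2/1.3 = 1.54, 2/1.5 = 1.33 and 2/1.6 = 1.25.

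**Step 5, the missing rule** (effect 0.5 at t2, none at t3):

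| Result | 0.3/0.5 | 0.5/0.6 | 0.6/0.8 |
|---|---|---|---|
| Three-level interaction as listed, univariate | 0.805 | 0.911 | 0.987 |
| t2 and t3 both significant | 0.037 | 0.041 | 0.038 |
| Holm, at least one | 0.818 | 0.888 | 0.936 |
| Average of t2 and t3 | 0.450 | 0.518 | 0.520 |

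**Step 6, no effect at all.** In the 20,000-trial runs the group-by-time and main-effect tests reject in 0.047 to 0.058 of trials. In the 4,000-trial runs the highest value is 0.060. Requiring both times rejects in 0.007, 0.008 and 0.016. Accepting either time without adjustment rejects in about 0.09 to 0.10.

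**The case against.** - **The SAP does not exclude a t0-by-time term, and some software may add it by default.** This stands. The power loss is conditional, but it then turns on a setting that the SAP leaves open.
- **The covariate does raise power for the group main effect.** True, but the SAP does not name that effect as the test of H1, and its raw estimate averages in t0.
- **The correlations are assumed.** They are. Even on the unfavourable reading, the univariate test falls clearly below 0.90 only at 0.3/0.5, and at a common correlation of 0.7 the loss is between one and two points. The cancellation and the missing rule need no assumed correlation.
- **The strictest rule does not restore power.** Requiring both times gives 0.79, 0.88 and 0.93, close to the listed interaction and below 0.90 in two of three settings. That is correct, but it supports a stronger claim than the interaction does.
- **The variance ratios in step 4 are not the loss of the three-level test.** They apply to one follow-up and only illustrate the cost of not adjusting.
- **The SAP promises alpha adjustment and effect sizes at t2 and t3.** It does, but neither says which result supports H1. Reading the conditional t-tests as following a significant overall test is natural, yet the SAP still does not say whether both must be significant.
- **The figures use 72 completers, whereas the intention-to-treat analysis imputes.** They approximate a completer analysis. The cancellation holds for complete data, including imputed data.

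**Conclusion.** The concern holds. On the text alone, t0 is both an outcome level and the covariate, no t0-by-time term is stated, and no deciding contrast for H1 is named.

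The open decision rule is the firmer part and rests on no assumption. Its practical size is the gap, when the effect is at t2 only, between rejection in 81% to 99% of trials and significance at both times in about 4%.

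The loss of power is conditional on t0 entering as a main effect only. In the three settings studied, with 72 per group and d = 0.5, the univariate test then loses about 14, 7 and 3 points (0.903 − 0.760, 0.955 − 0.884, 0.977 − 0.943), and the loss shrinks further at higher correlations. Type I error of each single test is not materially affected. This should be corrected before the data are analysed, because the model decides the primary outcome and ten secondary outcomes.

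**What to change.** Replace the first bullet of the H1 to H11 plan in section 5.2 with wording such as:

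> Outcome levels are t2 and t3 only; t0 enters only as covariate. The model (repeated-measures ANCOVA or mixed model) contains group, time, group × time, t0 and t0 × time. Adjusted differences between groups at t2 and t3 are reported with 95% confidence intervals and Cohen's d, and the SD used for d is stated. H1 is decided by [rule], [one- or two-sided]. H2 to H11 use the same model. Group × time in this model tests only whether the effect differs between t2 and t3.

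The team should name one rule in advance:
- **(a) t2 and t3 both significant, each at 0.05.** This is closest to H1 as worded. Power is 0.79, 0.88 and 0.93, so it misses the planned 0.90 in two of the three settings.
- **(b) t2 and t3 as two Holm-adjusted tests, the claim limited to the times that reject.** Power for at least one is 0.92, 0.96 and 0.97; for both it is 0.78, 0.88 and 0.93.
- **(c) The average over t2 and t3.** Power is 0.95, 0.98 and 0.98, but only 0.45, 0.52 and 0.52 if the effect is at t2 only.

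If three outcome levels are kept, add t0 × time explicitly and still name the rule.

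The cost is SAP wording and a few lines of code. No new data are needed, and neither the sample size nor the imputation changes.

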### 2.1. STUDY DESIGN

Randomized Controlled Trial with 240 participants working as healthcare professionals (120 in intervention, 120 in waitlist control group), monocentric study, duration: 14 months, study design chosen to evaluate long-term effects of our training)

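### For H1 to H11 the SAP does not carry the t0 covariate into the t2 and t3 comparisons; read literally, these are valid but less precise than they need to be

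*SAP*

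**What the plan says.** SAP section 4.4 words H1 to H11 as group differences at both t2 and t3 relative to t0. H1 begins "The intervention will significantly increase resilience, measured with the SR Score".

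Section 5.2 examines all eleven outcomes with a mixed ANCOVA: group as between-subjects factor, time (t0, t2, t3) as within-subjects factor, and the t0 value "included as a covariate to increase test power". Two further bullets follow. One reads "If applicable, post-hoc $t$ -tests will be conducted". The other plans Eta² for the ANCOVA, a between-group Cohen's d at t2 and at t3, and a Cohen's d for the intervention effect.

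The SAP does not say whether the t-tests use raw scores, change scores or t0-adjusted means, or whether d is raw or adjusted. It gives no condition for the words *if applicable*.

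**The concern.** An overall F test for group, or for group by time, does not show at which visit the groups differ. The statements about t2 and t3 will therefore rest on the follow-up t-tests and on d. If those are plain two-sample comparisons, the time-specific results leave out the covariate that was added one bullet earlier to gain power.

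The literal reading is the natural one. Section 5.1 uses t-tests for ordinary independent-samples baseline comparisons, and section 5.2 uses them for within-group pre-post comparisons under H13 and H14. Planned contrasts are named for H12 but not for H1 to H11.

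At stake are the precision of the t2 and t3 estimates for the primary outcome and ten secondary outcomes, and whether those estimates agree with the adjusted analysis above them. The choice also stays open until the data are seen.

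**Working it through.** **Inputs**
- Standardised difference 0.50: section 2.5, "we assume a medium effect here".
- Design: "a medium effect size, a significance level of 0.05 and a power of 0.90" (section 2.5). Sidedness is not stated; two-sided is used below.
- Allocation: "120 in intervention, 120 in waitlist control group" (section 2.1).
- Dropout 40% (section 2.5): 120 × 0.6 = 72 completers per group.
- Section 5.1 also plans an intention-to-treat analysis with imputation, so 120 per group is taken as the upper bound.
- Correlation r between t0 and the later score: not in the SAP. **Assumed** 0.3 to 0.7.

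**The plan's own figure.** Section 2.5 gives 74 per group and a total of 146, although 2 × 74 = 148. A noncentral-t calculation for 0.50, alpha 0.05 and power 0.90 gives 86 per group two-sided and 70 one-sided. A one-sided Wilcoxon-Mann-Whitney test with efficiency 3/π gives 73 per group, total 146. The SAP names neither that test nor a sidedness. None of these calculations includes a gain from the covariate.

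**Unadjusted t-test at one time point.** Noncentrality = d × √(n/2), with 2n − 2 degrees of freedom.
- n = 72: 0.50 × √36 = 3.00, power 0.846.
- n = 120: 0.50 × √60 = 3.87, power 0.971.

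**t0-adjusted contrast at the same time point.** The residual variance falls by the factor 1 − r², so noncentrality = d × √(n/2) / √(1 − r²), with one degree of freedom fewer. For n = 72 and r = 0.5 this is 3.00 / √0.75 = 3.46.

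| Assumed r | 72 per group: unadjusted | adjusted | 120 per group: unadjusted | adjusted |
|---|---|---|---|---|
| 0.3 | 0.846 | 0.878 | 0.971 | 0.981 |
| 0.5 | 0.846 | 0.931 | 0.971 | 0.994 |
| 0.7 | 0.846 | 0.987 | 0.971 | above 0.999 |

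The loss is about 3, 8 to 9, and 14 points at 72 per group, and 1 to 3 points at 120. A simulation with 4,000 runs at 72 per group agrees: 0.847 against 0.875, 0.852 against 0.933, and 0.853 against 0.988.

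**Sensitivity**
- Number per group for power 0.90: 86 unadjusted; 78, 65 and 44 adjusted.
- Illustrative alpha of 0.025 per time point, 72 per group: 0.768 against 0.809, 0.883 and 0.973. The SAP says alpha will be adjusted for multiple testing but names no method.
- Illustrative smaller effect of 0.35: with 72 per group, 0.550 against 0.590, 0.673 and 0.832; with 120 per group, 0.770 against 0.808, 0.877 and 0.966. The small loss at 120 per group therefore depends on the effect being as large as 0.50.
- t-test on change from t0, 72 per group: 0.712, 0.846 and 0.970. The adjusted contrast is more powerful at each assumed correlation.

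**Effect on d.** The standard error of the t0 group difference is √(2/72) = 0.17 SD. A chance imbalance of 0.2 SD with r = 0.5 shifts an unadjusted d by about 0.5 × 0.2 = 0.1, one fifth of the planned 0.50.

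**The case against.** The strongest reply is that the SAP never calls these t-tests unadjusted. The bullet stands directly below the adjusted ANCOVA, and a t-test of covariate-adjusted means fits its wording. So would a test on change, since the hypotheses are framed relative to t0. This stands: a reader might infer that the SAP prescribes dropping the covariate, but it is only silent. The power loss applies if the silence is filled in the literal way.

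Other parts of the reply also stand:
- Under randomisation an unadjusted t-test is valid. A reader might infer bias, but the issue is precision and consistency. A t0 imbalance enters d only in proportion to the correlation.
- Cohen's d is an estimate. It can lose precision but has no power to lose.
- Eta² is not the only planned summary. Section 5.2 also plans a Cohen's d for the intervention effect and one at each time point, and *if applicable* does not govern these.
- The ANCOVA is named as the analysis for H1 to H11 and the t-tests are labelled post hoc, which implies an order between them.
- The sample size claims no covariate gain, so the design does not depend on it. If the test were one-sided, the unadjusted comparison would have power 0.910 at 72 per group.

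Finally, the contrasts cannot simply be taken from the model as written, because t0 is both a level of the time factor and the covariate. That is correct, and the fix must deal with it. Correcting the model alone would still leave the follow-up bullet and d unspecified.

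**Conclusion.** The point holds as one of efficiency and specification. For the two time points at which H1 to H11 are claimed, the SAP names only conditional t-tests and a between-group d, and carries the t0 covariate into neither. Followed literally, this costs about 3 to 14 points of power with 72 per group and 1 to 3 points with 120. These figures assume a standardised difference of 0.50, a two-sided 0.05 test and a t0-outcome correlation of 0.3 to 0.7. The correlation is not in the SAP, and at the lower end the loss is small.

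The documents do not support the stronger conclusions that unadjusted tests are prescribed, that the results would be biased, or that the overall ANCOVA loses power for this reason. The change is still worth making: the t0 value is already collected, and the adjusted contrast is more precise at any correlation in this range.

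**What to change.** Replace the post-hoc bullet for H1 to H11 in section 5.2 with:

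> Group differences at t2 and at t3 are always estimated as t0-adjusted contrasts, each with a 95% confidence interval, from the ANCOVA with t2 and t3 as the outcome time points and t0 as covariate only.

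In the effect-size bullet, define the standardised difference at t2 and at t3 as the adjusted mean difference divided by the pooled t0 SD, and label any unadjusted d as descriptive only.

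The cost is SAP wording. No new data or participants are needed. The edit does require that the model treat t0 as covariate only, so both changes should be made together.

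### H12 predicts a gain kept to 12 months, but its only unconditional test is an omnibus ANOVA that responds alike to a kept and a lost gain; the contrasts that could decide it are optional and unnamed

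*SAP*

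**What the plan says.** SAP section 1.2 makes effects up to one year after the intervention an objective. Section 4.4 turns this into H12: in the intervention group resilience is improved at t2, and "these improvements should be maintained at the respective follow-ups", meaning t3, t4 and t5, possibly to a lesser degree. By section 2.6, t3 is 3 months after the post-measurement, and t4 and t5 are 6 and 12 months after it.

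H12 is the only stated hypothesis that reaches t4 and t5. H1 to H11 stop at t3, H13 and H14 concern state measures during training, and H15 concerns t2. Other longitudinal effects are exploratory.

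For H12, section 5.2 says the effect from t0 to t5 "within the intervention group will be tested using a repeated measures ANOVA". It adds that, where applicable, post-hoc t-"tests and planned contrasts will be conducted" and that effect sizes will be calculated. It names no pair of time points, no condition that triggers the contrasts and no degree of retention that counts as maintained. For multiple testing in general, alpha "will be adjusted accordingly", with no method given.

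**The concern.** The hypothesis has a direction and is specific to each follow-up. The test that is certain to be run has neither property: a repeated-measures F test rejects for any departure from a flat profile. A gain at t2 that has gone by t3 is such a departure, and so is a fall below baseline.

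The follow-up comparisons could settle the matter, but which of them settles it is left open until the data are seen. The one-year claim, which no other hypothesis carries, therefore has no fixed criterion. A significant F could be reported as support for H12 when the pattern behind it contradicts H12.

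**Working it through.** **The plan's own figure.** The SAP gives no power or sample size for H12, so there is none to reproduce. Its figure of 74 per group (section 2.5) belongs to the between-group comparison. A one-sided Wilcoxon-Mann-Whitney calculation comes close to it (73 per group, N = 146, power 0.902), though the SAP states neither that test nor one-sidedness. Nothing below depends on it.

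**Inputs from the SAP**
- Intervention arm: 120 (section 2.1). Dropout: 40% (section 2.5). Remaining: 120 × 0.60 = 72.
- Alpha: 0.05.
- Time points: t0 to t5. Because t1 is exploratory (section 5.3), both six and five time points were run.

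**Assumptions not in the SAP**
- A within-group gain of 0.5 SD at t2. This borrows the size of g = .50 from section 2.5, which is a between-group effect.
- t1 at 0.25 SD when it is included.
- Equal variances and equal correlations ρ of 0.3, 0.5 or 0.7.

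**Step 1: the two profiles look the same to the F test.** With SD = 1, the noncentrality is λ = n · Σ(μj − μ̄)² / (1 − ρ).
- Wholly lost from t3 (0, 0.25, 0.5, 0, 0, 0): mean 0.125; Σ = 4 × 0.015625 + 0.015625 + 0.140625 = 0.21875.
- Fully kept (0, 0.25, 0.5, 0.5, 0.5, 0.5): mean 0.375; Σ = 0.140625 + 0.015625 + 4 × 0.015625 = 0.21875.
- Without t1, lost (0, 0.5, 0, 0, 0) and kept (0, 0.5, 0.5, 0.5, 0.5) both give 0.16 + 4 × 0.01 = 0.20.

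The sums are equal, so the power is equal.

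**Step 2: power of the omnibus F at n = 72, the same for lost and kept**

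| ρ | λ, six points | Power, six points | λ, five points | Power, five points |
|---|---|---|---|---|
| 0.3 | 72 × 0.21875 / 0.7 = 22.5 | 97% | 72 × 0.20 / 0.7 = 20.6 | 97% |
| 0.5 | 31.5 | 99.7% | 28.8 | 99.5% |
| 0.7 | 52.5 | 100% | 48.0 | 100% |

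The exact equality needs equal correlations. Under AR(1) correlation with the Greenhouse-Geisser correction, simulation of the wholly lost profile still rejects in 94% (ρ = 0.5) and 99% (ρ = 0.7) of trials.

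**Step 3: a contrast against t0 separates the cases.** For t5 − t0 the noncentrality is δ√72 / √(2(1 − ρ)). At ρ = 0.5 this is 4.24 for δ = 0.5 and 2.12 for δ = 0.25. Two-sided at 0.05, without adjustment:

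| True t5 − t0 | ρ = 0.3 | ρ = 0.5 | ρ = 0.7 |
|---|---|---|---|
| 0 (lost) | 5% | 5% | 5% |
| 0.25 SD (half kept) | 42% | 55% | 77% |
| 0.5 SD (kept) | 94% | 99% | 100% |

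**Step 4: the cost once multiplicity is controlled.** Simulation at n = 72 and ρ = 0.5 to 0.7, with the four contrasts t2, t3, t4 and t5 against t0:
- Half the gain kept from t3 on: t5 is claimed in about 30% to 58% of trials with the fixed sequence t2, t3, t4, t5, and in about 44% to 70% with Holm.
- Gain fully kept: about 96% or more with either.

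At ρ = 0.3 the rates are lower. Bonferroni over t3, t4 and t5 alone gives 26% (half kept) and 87% (fully kept) for t5.

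**The case against.** The strongest reply is that the ANOVA is not the whole H12 analysis. Section 5.2 adds post-hoc t-tests and planned contrasts, and it lists planned contrasts for H12 but not for H1 to H11. It also requires descriptive statistics, effect sizes and an adjusted alpha. Nowhere does it say that a significant F confirms H12, and a reader who saw the follow-up means back at baseline could not honestly report maintenance. This stands against any claim that the plan cannot answer the long-term question: that holds for the F test alone. It does not supply the missing rule, because the contrasts are conditional and unnamed. The SAP can be exact where it chooses, since H13 and H14 name every pair of measurements compared.

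Two stronger readings are tempting and should be resisted.
- A reader might infer that a non-significant difference between t2 and t5 would be taken as maintenance. No such rule is written, and H12 itself allows a smaller effect later. It is only a misuse that the open wording does not exclude.
- A reader might infer that the ANOVA will rest on completers alone, given the expected dropout. Section 5.1 plans imputation for the intention-to-treat analysis, so this does not follow.

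It is also fair to say that H12 is a within-group hypothesis and that the randomised comparisons in H1 to H11 are untouched.

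**Conclusion.** The point holds in limited form. The one test that H12 is sure to receive cannot tell the hypothesis from its failure, and the SAP does not fix which of the optional comparisons decides it. The mismatch itself follows from the form of the test. The rates of 97% to 100% rest on the assumed 0.5 SD within-group gain, 72 participants and equal correlations of 0.3 to 0.7. They mean that the F test is very likely, not certain, to be significant after a complete loss.

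This goes beyond missing detail, because a better-matched test can be named at little cost. It is worth correcting, since H12 alone carries the one-year objective, but it does not bear on the primary between-group result.

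**What to change.** In section 5.2, make the contrasts of t2, t3, t4 and t5, each against t0, the decisive and unconditional analysis of H12. Name the multiplicity method, for example Holm or the fixed sequence t2, t3, t4, t5 at 0.05. Keep the omnibus ANOVA as descriptive. Then state that:
- persistence is claimed at a follow-up only if its contrast against t0 is significant, under the chosen method, in the direction of improvement;
- the t5-minus-t2 change is reported with its confidence interval as the measure of loss, and a non-significant t2-versus-t5 difference is not read as maintenance;
- the result is worded as within-group change.

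The work is a few lines of SAP text and routine contrasts. The real cost is that persistence at t5 becomes harder to claim when the gain fades, by the amounts in step 4 of the working. Holm loses less at t5 than the fixed sequence in the half-kept case, because the fixed sequence needs every earlier contrast to succeed first. The choice should be made before the data are seen.
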